15.1 Serious Adverse Event (SAE) Reporting

An adverse event is considered serious if it results in ANY of the following outcomes:

- Death
- A life-threatening adverse event
- An adverse event that results in inpatient hospitalization or prolongation of existing hospitalization
- A persistent or significant incapacity or substantial disruption of the ability to conduct normal life functions
- A congenital anomaly/birth defect
- Important Medical Events (IME) that may not result in death, be life threatening, or require hospitalization may be considered serious when, based upon medical judgment, they may jeopardize the patient or participant and may require medical or surgical intervention to prevent one of the outcomes listed in this definition

Note: Hospital admission for a planned procedure/disease treatment is not considered an SAE.

SAE reporting is required as soon as the participant starts investigational treatment/intervention. SAE reporting is required for 30 days after the participant's last investigational treatment/intervention. Any event that occurs after the 30-day period that is unexpected and at least possibly related to protocol treatment must be reported.

Please note: Any SAE that occurs prior to the start of investigational treatment/intervention and is related to a screening test or procedure (e.g., a screening biopsy) must be reported.

All SAEs must be submitted in PIMS. If an SAE requires submission to the HRPP Office per [IRB SOP RR-408 'Reporting of Serious Adverse Events.'](#) the SAE report must be submitted within 5 calendar days of the event. All other SAEs must be submitted within 30 calendar days of the event.

The report should contain the following information:

- The date the adverse event occurred
- The adverse event
- The grade of the event
- Relationship of the adverse event to the treatment(s)
- If the AE was expected
- Detailed text that includes the following
 - An explanation of how the AE was handled
 - A description of the participant's condition
 - Indication if the participant remains on the study
- If an amendment will need to be made to the protocol and/or consent form
 - If the SAE is an Unanticipated Problem

15.2 External SAE Reporting

SAE Reporting to Incyte

The Principal Investigator (PI) must report all SAEs to Incyte within 24 hours of learning of an event, regardless of the PI's causality assessment. This notification should be provided on a completed SAE form. SAE reporting for each subject begins the day the informed consent is signed by the patient and within 30 days after subject has completed or discontinued from the study or has taken last dose of the study drug, or as described in the protocol.

SAEs, occurring using Incyte study drug, are reported in accordance with the effective protocol. SAEs occurring with any other commercial drug are reported to the manufacturer of that drug in accordance with regulations and protocol.

Initial SAEs and/or subsequent follow-up reports should be reported via email to [contact] or fax(+) [name]. SAE reports should be for a single subject. SAE forms should be sent with a cover sheet and any additional attachments.

All SAEs incurred while a patient is on study will be reported to the IRB at MSKCC and Incyte. All SAEs and relevant laboratory findings will be reported to the principal investigator immediately. All information regarding SAEs must be recorded on the form provided. Patient suffering SAEs must be carefully followed and all follow-up information also recorded.

All life-threatening and lethal known, unknown, or suspected reactions must be reported to the principal investigator. It is the treating physician's responsibility to investigate and report the date and cause of death of any patient entered on this trial.

Reporting of Pregnancy to Incyte

An "Initial Pregnancy Report" or equivalent must be completed in full and emailed to [contact] or faxed to (+) [name] within 24 hours of discovery of a pregnancy of a subject who has taken the Incyte product. The "Follow-up Pregnancy Report Form" or equivalent must be completed and emailed to [contact] or faxed to (+) [name] within 30 days after delivery, so that Incyte is provided with information regarding the outcome of the pregnancy. If the pregnancy results in any events which meet the serious criteria (i.e., miscarriage or termination), the SAE reporting process needs to be followed and the timelines associated with a SAE should be followed.

The SAE report should be completed as per above instructions. If appropriate, the report will be forwarded to the FDA by the IND Office.

15.3 Pregnancy

Lenalidomide is related to thalidomide. Thalidomide is known to cause severe, life-threatening human birth defects. Lenalidomide is known to cause birth defects in animals. If lenalidomide is taken during pregnancy, it may cause birth defects or death to any unborn baby. Females must not become pregnant or breastfeed while taking lenalidomide. Because lenalidomide carries a risk of causing thromboembolism, it is recommended that patients avoid taking oral contraceptives or hormone replacement therapy before discussing with the investigator and considering risks and benefits of these choices. In men taking lenalidomide, the drug is present in the semen at very low levels for three days after discontinuing, and may be present longer in those with impaired drug elimination (eg, renal dysfunction). All patients must adhere to the contraception requirements of the Revlimid REMS program. Patients should not donate blood during treatment or for 28 days following discontinuation of lenalidomide.

If a patient inadvertently becomes or is suspected to have become pregnant while receiving study treatment, the patient will immediately be removed from the study. The investigator will follow the reporting and monitoring requirements of the Revlimid REMS program.

16.0 PROTECTION OF HUMAN PARTICIPANTS

Potential risks to human subjects include drug-related toxicity; pain and discomfort associated with therapy; treatment side effects; phlebotomy; and possible psychologic discomfort from the stresses associated with obtaining imaging studies.

The side effects and potential toxicities of all agents are listed in section 15.0. All efforts will be made to avoid any complication by completely reviewing patients' symptoms, providing appropriate management, and monitoring blood tests.

If an AE occurs, the patient will first contact the primary oncologist or the principal investigator. At nights and weekends, there is an oncology physician on call at all times. Patients may either call or come directly to the Urgent Care Center at Memorial Hospital (or to their local emergency room) to be seen.

Costs to the patient (third party insurer) will include the cost of blood tests and diagnostic studies, office visits, those admissions which may be required as a consequence of treatment-related complications, and the costs of obtaining lenalidomide.

16.1 Privacy

MSK's Privacy Office may allow the use and disclosure of protected health information pursuant to a completed and signed Research Authorization form. The use and disclosure of protected health information will be limited to the individuals/entities described in the Research Authorization form. A Research Authorization form must be approved by the IRB and Privacy Board (IRB/PB).

The consent indicates that individualized, de-identified information collected for the purposes of this study may be shared with other qualified researchers. Only researchers who have received approval from MSK will be allowed to access this information, which will not include protected health information such as the participant's name, except for dates. It is also stated in the Research Authorization that their research data may be shared with others at the time of study publication.

16.2 Data Management

A Clinical Research Associate (CRA) will be assigned to the study. The responsibilities of the CRA include project compliance, data collection, abstraction and entry, data reporting, regulatory monitoring, problem resolution and prioritization, and coordinate the activities of the protocol study team.

The data collected for this study will be entered into a secure database (Medidata) at MSKCC. Source documentation will be available to support the computerized patient record. Final data sets for publication are required to be locked and stored centrally for potential future access requests from outside entities.

16.3 Quality Assurance

Registration reports will be generated on an ongoing basis to monitor patient accruals and completeness of registration data. Routine data quality reports will be generated to assess missing data and inconsistencies. Accrual rates and extent and accuracy of evaluations and follow-up will be monitored periodically throughout the study and potential problems will be brought to the attention of the study team for discussion and action.

Random-sample data quality and protocol compliance audits will be conducted by the study team at a minimum of two times per year and more frequently if indicated.

Memorial Sloan Kettering Cancer Center
[name]
[name]

16.4 Data and Safety Monitoring

The Data and Safety Monitoring Plan utilized for this study must align with the [MSK DSM Plan](#) where applicable.

The Data and Safety Monitoring (DSM) Plans at Memorial Sloan Kettering were approved by the National Cancer Institute in August 2018. The plans address the new policies set forth by the NCI in the document entitled "[Policy of the National Cancer Institute for Data and Safety Monitoring of Clinical Trials](#)."

There are several different mechanisms by which clinical studies are monitored for data safety and quality. At a departmental/PI level, there exist procedures for quality control by the research team(s). Institutional processes in place for quality assurance include protocol monitoring, compliance and data verification audits, staff education on clinical research QA, and two institutional committees that are responsible for monitoring the activities of our clinical trials programs. The committees: *Data and Safety Monitoring Committee (DSMC)* for Phase I and II clinical trials, and the *Data and Safety Monitoring Board (DSMB)* for Phase III clinical trials, report to the Deputy Physician-in-Chief of Clinical Research.

The degree of monitoring required will be determined based on level of risk and documented.

The MSK DSMB monitors phase III trials and the DSMC monitors non-phase III trials. The DSMB/C have oversight over the following trials:

- MSK Investigator-Initiated Trials (IITs; MSK as sponsor)
- External studies where MSK is the data coordinating center
- Low risk studies identified as requiring DSMB/C review

The DSMC will initiate review following the enrollment of the first participant, or by the end of the year one if no accruals, and will continue for the study lifecycle until there are no participants under active therapy and the protocol has closed to accrual. The DSMB will initiate review once the protocol is open to accrual.

18.0 APPENDICES

Memorial Sloan Kettering Cancer Center
[name]
[name]

Appendix A: Karnofsky performance status^{33,34}

%	Performance status description
100	Normal. No complaints. No evidence of disease.
90	Able to carry on normal activity. Minor signs or symptoms of disease.
80	Normal activity with effort. Some signs or symptoms of disease.
70	Cares for self. Unable to carry on normal activity or to do active work.
60	Requires occasional assistance, but is able to care for most of their personal needs.
50	Requires considerable assistance and frequent medical care.
40	Disabled. Requires special care and assistance.
30	Severely disabled. Hospitalization is indicated although death is not imminent.
20	Hospitalization necessary, very sick, active supportive treatment necessary.
10	Moribund. Fatal processes progressing rapidly.
0	Dead.

Memorial Sloan Kettering Cancer Center
[name]
[name]

Appendix B: Cockcroft-Gault CrCl^{5,36}

1. Determine weight to be used:

- a. Calculate ideal body weight (IBW) in kilograms:
 - i. Female: $45.5 + (2.3 \times (\text{height, inches} - 60))$
 - ii. Male: $50 + (2.3 \times (\text{height, inches} - 60))$
- b. If IBW > total (actual) body weight (TBW), use TBW in kilograms
- c. If IBW \leq TBW:
 - i. If $\frac{IBW}{TBW} < 1.3$, use IBW in kilograms
 - ii. If $\frac{IBW}{TBW} \geq 1.3$, use adjusted body weight (AdjBW) in kilograms:
$$[\text{IBW, kilograms}] + (0.4 \times [\text{TBW, kilograms}] - [\text{IBW, kilograms}])$$

[figure not shown]
2. Calculate CrCl using weight determined in step 1:

$$CrCl \left(\frac{ml}{mm} \right) = \frac{(140 - [\text{age, years}]) \times [\text{weight, kilograms}]}{72 \times \text{serum creatinine, } \frac{mg}{dl}} \times (0.85 \text{ only if female})$$

Memorial Sloan Kettering Cancer Center
[name]
[name]

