6.1 Participant Inclusion Criteria

Patients must meet all of the following criteria to be eligible for inclusion in this study:

- Age ≥ 18 years at the time of signing Informed Consent
- Karnofsky performance status (KPS) ≥ 70% (see Appendix A)
- Pathologically confirmed diagnosis of R/R MCL
- Previously treated with at least one prior line of systemic therapy for MCL, at least one of which must have been a BTKi
- If patient previously received CD19-directed therapy (such as CAR-T therapy), then there must be evidence of CD19 expression confirmed by immunohistochemistry or flow cytometry per institutional guidelines. This must be confirmed on a biopsy performed after receipt of CD19-directed therapy.

- Previous systemic chemotherapy must have been discontinued at least 2 weeks prior to C1D1 and previous anti-cancer radiation therapy or targeted therapy must be discontinued prior to initiation of treatment on study
 - All adverse effects should resolve to grade 1 or baseline (excluding alopecia)
- Presence of evaluable disease
- Adequate bone marrow and organ function:
 - Absolute neutrophil count (ANC) 2: 1,500 cells/mcL, unless felt to be secondary to underlying MCL
 - Platelet count 2: 90,000 cells/mcL, unless felt to be secondary to underlying MCL
 - Renal function assessed by calculated Cockcroft-Gault creatinine clearance (CrCl; see Appendix B) 2: 30ml/min. See 10.0 Treatment Plan, Table 10-1, for lenalidomide dose adjustment for CrCl 2: 30ml/min and < 60ml/min.
 - Hepatic function:
 - Total bilirubin < 2.5x upper limit of normal (ULN), unless secondary to Gilbert's syndrome or documented liver involvement by lymphoma. Patients with Gilbert's syndrome or documented liver involvement by lymphoma may be included if total bilirubin is ≤ 5x ULN.
 - Aspartate transaminase (AST) and alanine transaminase (ALT) ≤ 3x ULN, unless secondary to documented liver involvement by lymphoma. Patients with documented liver involvement by lymphoma may be included if AST and ALT are ≤ 5x ULN.
- Willingness to receive adequate prophylaxis and/or therapy for thromboembolic events, unless contraindicated in the opinion of the investigator
- Willingness to undergo confirmatory procedures for assessment of disease status and experimental studies as required by protocol, including bone marrow (BM) aspiration/biopsy, gastrointestinal endoscopy/colonoscopy with biopsy, and/or biopsy of other tissue when appropriate and medically feasible

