10.2 Lenalidomide

Lenalidomide will be self-administered by patients orally on days 1-21 of each 28-day cycle of induction (cycles 1 through 12). Patients will be instructed to take each dose of lenalidomide at about the same time each day with approximately 8 ounces (240ml) of water, without regard to food. Lenalidomide must be swallowed whole; patients should not open or break the capsules. If a dose is missed, the dose may be taken if within 12 hours of usual dosing time. If more than 12 hours have elapsed since usual dosing time, the patient should skip the missed dose and take the next dose at the usual dosing time. If a patient vomits after taking a dose, the dose should not be made up.

Research personnel will review the dosing instructions with patients. Patients will be provided with a medication diary and asked to record the drug administration. Patients will be asked to bring any unused drug and empty drug containers to the research personnel at the beginning of each cycle. Site staff will count and record the number of used and unused drug at the beginning of each cycle and reconcile their findings with the patient diary.

The daily dose of lenalidomide in patients with normal renal function (CrCl 2: 60ml/min) is 20mg. Renal adjustments are outlined in Table 10-1. In patients with impaired renal function at baseline who qualify for study inclusion (CrCl < 60ml/min but 2: 30ml/min), the daily dose of lenalidomide is 10mg daily, with escalation to 15mg daily permitted after 2 cycles if tolerating treatment in the opinion of the investigator. Patients who subsequently develop severe renal dysfunction (CrCl 30ml/min) after initiation of study treatment may continue treatment with lenalidomide at a reduced dose as noted in Table 10-1. Note that renal

dysfunction resulting from toxicity suspected to be related to tafasitamab and/or lenalidomide (eg, due to tumor lysis syndrome) may warrant interruption and/or discontinuation of either or both drugs, as outlined in Table 10-4.

Table 10-1: Lenalidomide dose adjustment for renal dysfunction prior to or after study initiation		
Cockcroft-Gault CrCl (see Appendix B)	Daily lenalidomide dose (days 1-21 of cycles 1-12)	Note
30ml/min and < 60ml/min	10mg	May increase to 15mg once daily after 2 cycles if tolerating treatment in the opinion of the investigator
Severe renal dysfunction after study treatment initiation*		
< 30ml/min not requiring dialysis	5mg once daily	

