10.5.6 Lenalidomide dose reductions for toxicity

If lenalidomide dosing was interrupted during the previous cycle, restarted at the next lower dose level during the same cycle in which it was interrupted, and did not require interruption for the remainder of the cycle, then that reduced dose level will be initiated on day 1 of the next cycle. There will be no more than one dose reduction from one cycle to the next.

A dose reduction of lenalidomide constitutes a 5mg decrease in the daily dose from the previous dose, including in patients who initiate treatment at a decreased dose due to renal dysfunction. Patients who are unable to tolerate the lowest dose of 5mg once daily should discontinue lenalidomide but continue treatment with tafasitamab alone.

Table 10-6: Lenalidomide dose reductions for toxicity		Note
Starting dose	20mg once daily days 1-21 of each 28-day cycle	In patients who required lenalidomide dose reduction for hematologic toxicity early in the treatment course due, in the opinion of the investigator, to bone marrow and/or splenic disease
Dose level -1	15mg once daily days 1-21 of each 28-day cycle	
Dose level -2	10mg once daily days 1-21 of each 28-day cycle	

Dose level -3	5mg once daily days 1-21 of each 28-day cycle	involvement, re-escalation to the previous dose level is permitted
Further reduction indicated	Discontinue	

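### Appendix B's adjusted-body-weight step cannot be reached as printed, so patients at 1.3 times ideal body weight or more have creatinine clearance calculated on ideal weight

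*Combined protocol and SAP*

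**What the plan says.** Appendix B, step 1, chooses the weight in three parts. Step 1a computes IBW from sex and height. Step 1b handles patients lighter than their ideal weight: "If IBW > total (actual) body weight (TBW), use TBW in kilograms". Step 1c handles everyone else, that is, IBW at or below TBW, and splits them in two. The first sub-step is "If $\frac{IBW}{TBW} < 1.3$, use IBW in kilograms". The second is "If $\frac{IBW}{TBW} \geq 1.3$, use adjusted body weight (AdjBW) in kilograms", followed by a formula for the adjusted weight (AdjBW). Step 2 puts the chosen weight into Cockcroft-Gault.

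The result is used in two places. Section 6.1 makes it an entry criterion: "Renal function assessed by calculated Cockcroft-Gault creatinine clearance (CrCl; see Appendix B") must be at least 30 ml/min. Section 10.2 and Table 10-1 make it the dosing rule. At 60 ml/min or above, lenalidomide starts at 20 mg. From 30 to below 60 ml/min, "the daily dose of lenalidomide is 10mg daily, with escalation to 15mg daily permitted after 2 cycles" if the investigator judges treatment to be tolerated. (The comparison signs in these sections are partly garbled in the extracted text; they are read here as at least 30 and at least 60.) No other section gives a weight rule for creatinine clearance (CrCl).

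**The concern.** The two sub-steps of 1c are meant to separate patients near their ideal weight from patients well above it. A ratio of ideal to total weight cannot do this in a branch that already requires ideal weight to be no larger than total weight. One sub-step is always true and the other is never true, so the AdjBW formula has no one to apply to.

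This is more than untidy drafting, because the appendix feeds two cut-offs with consequences. A clearance that is too low can put a patient in the 10 mg row of Table 10-1 instead of starting at 20 mg, or below the entry limit. Section 10.5.6 says "A dose reduction of lenalidomide constitutes a 5mg decrease in the daily dose from the previous dose", with 5 mg as the lowest dose. A patient who starts at 10 mg and is not escalated therefore has one reduction step (5), against three from 20 mg (15, 10, 5). Lenalidomide is half of the regimen under test.

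**Working it through.** The appendix has no worked example to reproduce, so the check has two parts: whether the step can be reached, and how large the difference is under the inferred rule.

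**Reachability.** Step 1c requires IBW ≤ TBW. Dividing by TBW gives IBW/TBW ≤ 1. Hence IBW/TBW < 1.3 always holds (1c-i), and IBW/TBW ≥ 1.3 never holds (1c-ii). A grid confirms this: both sexes, heights 55 to 80 in, TBW 30 to 200 kg in 0.5 kg steps. Of 14,072 combinations with IBW ≤ TBW, 0 meet 1c-ii. With the ratio turned round to TBW/IBW ≥ 1.3, 12,039 do. Grid points are not a patient distribution; they show only that inverting the ratio makes the step usable.

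**Inferred rule (assumption).** Use AdjBW = IBW + 0.4 × (TBW − IBW) when r = TBW/IBW ≥ 1.3, and IBW when r < 1.3. The printed and inferred rules agree for r < 1.3.

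**Size for r ≥ 1.3.** CrCl is proportional to the weight used. The inferred weight is k × IBW with k = 1 + 0.4 × (r − 1). The printed rule uses IBW, so it understates CrCl by 1 − 1/k. The dose row changes when the printed-rule CrCl lies from 60/k to below 60. Eligibility changes when it lies from 30/k to below 30.

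| r | k | Understatement | Dose row changes (ml/min) | Eligibility changes (ml/min) |
|---|---|---|---|---|
| 1.3 | 1.12 | 10.7% | 53.6 to <60 | 26.8 to <30 |
| 1.5 | 1.20 | 16.7% | 50.0 to <60 | 25.0 to <30 |
| 2.0 | 1.40 | 28.6% | 42.9 to <60 | 21.4 to <30 |

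**Illustration (assumed patient).** Man, 70 in, 110 kg, aged 68 (the median age at presentation given in section 3.0).

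- IBW = 50 + 2.3 × (70 − 60) = 73 kg; r = 110/73 = 1.51.
- AdjBW = 73 + 0.4 × (110 − 73) = 87.8 kg.
- CrCl = (140 − 68) × weight / (72 × creatinine) = weight / creatinine, since 140 − 68 = 72.
- Creatinine 1.3 mg/dl: printed rule 73/1.3 = 56.2 ml/min (10 mg start); inferred rule 87.8/1.3 = 67.5 ml/min (20 mg start).
- Creatinine 2.5 mg/dl: printed rule 73/2.5 = 29.2 ml/min (not eligible); inferred rule 87.8/2.5 = 35.1 ml/min (eligible on this criterion, 10 mg start).

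**Design.** The Simon boundaries in section 14.0 (more than 6 responders of 19 to continue, 17 of 39 at the end) are response counts judged against fixed rates of 30% and 50%. CrCl does not enter their calculation.

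**The case against.** The strongest reply is that this is a self-revealing slip. An adjusted-weight step nested under IBW ≤ TBW makes sense only with TBW/IBW, and staff who know the usual calculation would probably apply it. Nothing in the documents shows that anyone has computed CrCl by the literal text. That stands, and it is why a recheck of past patients is needed only if the literal rule was used. It does not remove the need to correct a rule that governs eligibility and dose: if staff do apply the usual rule, practice departs from the written protocol.

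A second reply is that the appendix text is damaged by PDF extraction. The clearance unit comes out as ml/mm, and the heading's citation reads 5,36 where the contents list has 35,36. The original page should be checked. But the ratio is printed the same way round on two separate lines, with comparison signs that fit together, so a reading fault would have had to invert both fractions identically. An authoring slip is likelier.

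A third reply is that the effect is narrow and cautious. This also stands. Literal use gives a lower dose or an exclusion, not an overdose. Escalation to 15 mg after two cycles recovers part of the dose. Tafasitamab is dosed on actual weight (section 10.1) and is not touched.

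Three stronger readings are tempting, and the documents do not support them:

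- A reader might infer that the adjusted-weight formula is itself wrong. As extracted, its bracket encloses 0.4 × TBW − IBW, so the whole formula collapses to 0.4 × TBW. A misplaced bracket in a typeset formula is a plausible extraction fault, and here there is no second line to corroborate it. It is something to confirm on the page, not an established error.
- A reader might infer that every patient at or above ideal weight gets a wrong clearance. Below 1.3 × IBW the inferred rule also uses IBW, so nothing changes for them.
- A reader might infer that patients have been underdosed or wrongly excluded. The documents give no weight, creatinine or CrCl distribution and no account of how CrCl was calculated in practice.

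**Conclusion.** Wrong as written. That step 1c-ii can never be met is a matter of logic and needs no assumption beyond the text as it stands. As a result, patients with TBW of at least 1.3 × IBW are calculated on IBW, not on adjusted weight.

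The size depends on one inference: that the intended test is TBW/IBW ≥ 1.3 with AdjBW = IBW + 0.4 × (TBW − IBW). On that basis CrCl is understated by 10.7% at the threshold, rising to 28.6% at twice ideal weight. It changes a decision only for patients at or above 1.3 × IBW whose clearance falls in the bands just below 60 or 30 ml/min. How many such patients there are cannot be stated. The error runs in the cautious direction, and the type I error, power and stopping boundaries are unaffected. It should be corrected because it sits in an operative rule and is cheap to mend.

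**What to change.** In Appendix B, change the ratio to TBW/IBW in both 1c-i and 1c-ii. In the same edit, confirm on the original page that the adjusted-weight formula reads IBW + 0.4 × (TBW − IBW), and correct the bracket if it does not. The two belong together, because inverting the ratio brings the formula into use.

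Then establish which rule was used in practice. If it was the literal one, recheck the CrCl eligibility decision (including any screen failures on CrCl) and the Table 10-1 dose row for patients with TBW of at least 1.3 × IBW. If the usual rule was used throughout, the text correction is enough.

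The cost is a two-line edit, one formula check and, at most, a recalculation limited to the heavier patients. Sample size and analysis do not change.

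### Appendix B's adjusted-body-weight formula reduces to 0.4 × total body weight; the printed trigger keeps it dormant, but used or half-corrected it would cut calculated CrCl by about 43% to 54%

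*Combined protocol and SAP*

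**What the plan says.** Appendix B sets out the Cockcroft-Gault calculation in two steps. Step 1 chooses a body weight:

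- Step 1b: a patient whose ideal weight exceeds actual weight uses actual weight.
- Step 1c covers everyone else, that is IBW ≤ TBW, and splits them by a ratio.
- Step 1c-i: "If $\frac{IBW}{TBW} < 1.3$, use IBW in kilograms".
- Step 1c-ii: "If $\frac{IBW}{TBW} \geq 1.3$, use adjusted body weight (AdjBW) in kilograms", with AdjBW given as "IBW, kilograms}] + (0.4 \times [\text{TBW, kilograms}] - [\text{IBW, kilograms", the second and third terms sharing one round bracket.

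Step 2 carries the choice forward: "Calculate CrCl using weight determined in step 1".

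Two parts of the protocol depend on the result. Section 6.1 makes it an entry criterion with a 30 ml/min limit: "Renal function assessed by calculated Cockcroft-Gault creatinine clearance (CrCl; see Appendix B". Section 10.2 separates the lenalidomide dose rows at 60 ml/min, and the first column of Table 10-1 is headed "Cockcroft-Gault CrCl (see Appendix B". By its title, that table applies both before and after study start.

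**The concern.** Step 1c-ii has two separate faults. The trigger decides who reaches the formula, and the formula decides what weight they get. This point is about the formula, but its consequence depends on the trigger.

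The formula starts from IBW, adds a bracket, and ends with IBW no longer in it. A patient at or above ideal weight would be given a calculation weight below ideal weight. An adjustment meant for that group should fall between ideal and actual weight.

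CrCl is proportional to the chosen weight, so any error in weight passes in full to the figure that decides entry and dose row. The practical risk is a partial repair. Someone who notices the impossible trigger will probably invert the ratio and then apply the formula as it stands. That would replace a modest departure with a larger one.

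**Working it through.** The documents give no worked AdjBW or CrCl value, so there is no stated figure to reproduce. The check is algebra on Appendix B, followed by examples.

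**1. The formula.** IBW + (0.4 × TBW − IBW) = 0.4 × TBW. Write r = TBW/IBW.

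- Printed weight = 0.4r × IBW. This is below IBW whenever r < 1/0.4 = 2.5.
- If 0.4 multiplies the whole difference, weight = IBW + 0.4 × (TBW − IBW) = (0.6 + 0.4r) × IBW. This lies between IBW and TBW for every r > 1.

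**2. The trigger.** Step 1c requires IBW ≤ TBW, so IBW/TBW ≤ 1. Step 1c-ii then requires IBW/TBW ≥ 1.3. Both cannot hold. A grid of IBW from 30 to 120 kg and TBW from 30 to 250 kg gave 0 combinations that reach the step. Patients with a ratio above 1 have already been sent to TBW by step 1b. Read literally, everyone in step 1c uses IBW.

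**3. Size, as ratios of CrCl.** The comparator is the weight with 0.4 applied to the difference.

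| r = TBW/IBW | Printed AdjBW: 0.4r/(0.6 + 0.4r) | Literal reading (IBW): 1/(0.6 + 0.4r) |
|---|---|---|
| 1.3 | 0.52/1.12 = 0.464 (54% lower) | 1/1.12 = 0.893 (11% lower) |
| 1.5 | 0.60/1.20 = 0.500 (50% lower) | 1/1.20 = 0.833 (17% lower) |
| 2.0 | 0.80/1.40 = 0.571 (43% lower) | 1/1.40 = 0.714 (29% lower) |

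**4. The jump at the cut-off.** If the ratio is read as TBW/IBW, a man with IBW 68.4 kg would use 68.4 kg just below 1.3 and 0.4 × 1.3 × 68.4 = 35.6 kg at 1.3.

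**5. Examples (patient values are assumptions).** At age 68, (140 − 68)/72 = 1, so CrCl = weight/creatinine, times 0.85 for a woman.

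- Man, 68 in, 100 kg: IBW = 50 + 2.3 × 8 = 68.4 kg, r = 1.46. Printed AdjBW = 40.0 kg. With 0.4 on the difference, 68.4 + 0.4 × 31.6 = 81.0 kg.
- Woman, 64 in, 80 kg: IBW = 45.5 + 2.3 × 4 = 54.7 kg, r = 1.46. Printed AdjBW = 32.0 kg. With 0.4 on the difference, 54.7 + 0.4 × 25.3 = 64.8 kg.

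| Patient, creatinine (mg/dl) | Printed AdjBW, if used | Literal reading (IBW) | 0.4 on the difference |
|---|---|---|---|
| Man, 1.1 | 36.4 | 62.2 | 73.7 |
| Man, 1.4 | 28.6 | 48.9 | 57.9 |
| Woman, 1.0 | 27.2 | 46.5 | 55.1 |
| Woman, 0.8 | 34.0 | 58.1 | 68.9 |

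Values are CrCl in ml/min. In the first row the printed AdjBW puts the man on the other side of 60 from both alternatives. In the second and third rows it fails the 30 ml/min limit where both alternatives pass. In the last row the literal reading and the re-bracketed value themselves fall on opposite sides of 60, so the trigger alone can also change the row.

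**The case against.** The strongest reply is that the formula does no harm as the text stands. A reader might infer from the algebra that the protocol already halves CrCl in heavy patients. The documents do not support that. The printed trigger is never met, so those patients are assigned IBW. The example man then has 62.2 or 48.9 ml/min, not 36.4 or 28.6, and stays in the same dose row as under the re-bracketed formula. This part of the reply stands, and it makes the formula error conditional. It does not remove it: a protocol that prints an AdjBW step means it to be used, and inverting the ratio is the obvious repair.

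The second reply is that the misplaced bracket may come from converting the PDF to text. Appendix B shows other damage: the CrCl unit reads ml/mm, the heading cites references 5 and 36 where the table of contents has 35 and 36, and a figure is missing directly after the formula. Against that, the brackets in the printed expression balance, and the nested brackets in the IBW formulas of the same step survived. Neither observation settles it, so the source PDF has to be checked first.

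The third reply is that the documents nowhere print the alternative formula, and the reference cited for the appendix is not available here. That is fair. The appendix's own logic shows that 0.4 × TBW cannot be an adjusted weight. Applying 0.4 to the difference is the bracketing that makes the step coherent, but the sponsor must confirm it.

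**Conclusion.** The point holds as a latent error. As transcribed, the AdjBW expression equals 0.4 × TBW and cannot work as an adjustment between ideal and actual weight. It has no effect under a literal reading, where patients at or above ideal weight use IBW and CrCl is about 11% to 29% below the re-bracketed value for TBW/IBW from 1.3 to 2.0. It takes effect if staff read the ratio as TBW/IBW, or if an amendment corrects the trigger alone. The shortfall is then about 54% down to 43% over the same range, enough to move patients across the entry limit or the dose-row boundary.

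This rests on the transcription being faithful and on the comparator applying 0.4 to TBW − IBW. The documents contain no calculated CrCl and no weight distribution. A reader should therefore not conclude that any patient has been excluded or placed in another row because of this formula. Nothing shows which calculation was used, and the share of patients affected is unknown.

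**What to change.** 1. Compare the AdjBW expression and the step 1c ratio with the source PDF.
2. If both are as transcribed, reconcile them in a single amendment. The trigger should be one that patients in step 1c can meet, and the AdjBW expression should give a weight between IBW and TBW. The bracketing that achieves this has 0.4 multiplying the difference TBW − IBW. Do not correct the trigger alone.
3. Confirm that Appendix B is then consistent with the entry criterion in section 6.1 and with section 10.2 and Table 10-1. No change to any limit, row or dose is proposed here.
4. Establish which calculation was actually used for patients already screened or enrolled, including screen failures on renal function, and recompute their CrCl under the reconciled text.

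The cost is one bracket and one ratio in an appendix, plus a spreadsheet check. The design plans 39 evaluable patients, so the re-check is small. The sample size, the two-stage boundaries and the endpoints are untouched.
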